**Corticosteroid Injections for the Treatment of Common Upper Extremity Pathologies,
With or Without Lidocaine: A Randomized Control Trial**

NTC# NCT03704584

Date: 7/9/2019

Project Summary

Title of Study: Corticosteroid Injections for the Treatment of Common Upper Extremity Pathologies, With or Without Lidocaine: A Randomized Control Trial

Principle Investigator: [name] MD

Co-Investigators: [name], [name], [name] MD, [name] MD, [name]

Study Coordinators: [name], [name], [name], [name]

Version date: 7/9/2019

Lay Summary: A tendon is a type of tissue that connects your muscles to your bones. These tissues help control actions such as running, jumping, grasping, and lifting. Without tendons, you wouldn't be able to control the movement of your body. A protective layer known as synovium covers tendons. This sheath produces fluid, which keeps the tendon lubricated and moving properly. Inflammation or swelling of the sheath is known as tendon sheath inflammation or tenosynovitis. This condition is often treated with an injection into or around the sheath. This injection often consists of a corticosteroid with or without lidocaine. Corticosteroid are drugs that decrease inflammation and are given for a number of orthopaedic conditions to decrease symptoms of the underlying disease. Lidocaine is also a drug that blocks the pain response, although it only blocks it momentarily. Our study aims to determine if corticosteroid injection alone is as effective as corticosteroid combined with lidocaine for the relief of tenosynovitis of the upper extremity.

Precis/Abstract:

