This will be a randomized control trial to study the efficacy of a combined lidocaine and corticosteroid injection on pain, range of motion, and patient reported outcomes versus a corticosteroid injection alone for the treatment of common upper extremity tendinopathies and nerve entrapments that are often treated with a combination of these injectates. Patients will be assigned randomly to a control group (corticosteroid injection alone) or the treatment group (lidocaine plus corticosteroid injection). At the initial injection a 10-point likert scale prior to and after the injection will be administered. The patients will be followed up at 6 weeks after the injection, at which time the Visual Analog Scale for pain (VAS-pain), range of motion (ROM), and patient reported outcome data will be collected and any complications will be noted. Patients will also utilize a pain journal to track VAS-pain over the first 7 post-injection days. We hypothesize that those who receive lidocaine plus corticosteroid injection will be non-inferior in regards to pain, range of motion (ROM), failure of injection requiring surgery, and patient reported outcome scores compared with patients who received corticosteroid injection alone.

Background and Significance:

Tenosynovitis is a common ailment of the upper extremity resulting in pain around the affected joint due to injury to the tendon sheath. One of the most common manifestations of tenosynovitis is trigger finger. Trigger finger is an extremely common pathology encountered by primary care providers and hand surgeons. Reported incidence of 28 cases per 100,000 has been documented [1]. This entity occurs when the contents of the flexor tendon sheath do not fit cleanly

within the sheath, causing friction on movement of the fingers. Progression from a clicking or locking sensation to complete inability to flex or extend the finger (hence the designation “trigger finger”) occurs over the course of the disease. Therefore, triggering may not be initially noted on exam. Pain from this pathology can be experienced at the proximal interphalangeal joint, the metacarpophalangeal joint, or even the palm [2]. Reported increases in rates have been documented in diabetics, cases of repetitive trauma, those with renal and thyroid disease, and individuals with inflammatory conditions [3].

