In addition, similar pathologies exist where the role of lidocaine remains vague. One such pathology is de Quervain tenosynovitis. de Quervain tendinopathy affects the abductor pollicis longus (APL) and extensor pollicis brevis (EPB) tendons in the first extensor compartment at the styloid process of the radius. It is characterized by pain or tenderness at the radial side of the wrist. Although de Quervain tendinopathy is often attributed to overuse or repetitive movements of the wrist or thumb, the cause is generally unknown. It most commonly affects women between the ages of 30-50 years old [28].

A small randomized trial found that glucocorticoid injections resulted in significantly better symptom improvement compared with placebo one week after injection [29]. Among those who responded to glucocorticoid injections, the beneficial effects were maintained during the 12-month follow-up period. Another randomized trial also found that splinting plus glucocorticoid injection was better than splinting alone [30]. Most patients experience pain relief after a single glucocorticoid injection [30, 31]. In patients with recurrent symptoms after initial relief with the

first glucocorticoid injection, a second injection may provide benefit. However, limited evidence is available about the role of lidocaine during these injections. We further aim to elucidate the role of corticosteroid and lidocaine versus corticosteroid alone in the treatment of de Quervain tenosynovitis.

Furthermore, the role of lidocaine with corticosteroid in the treatment of a number of other tenosynovitides remains ambiguous. These include tenosynovitis of the shoulder, biceps, elbow, wrist, thumb, carpometacarpal, midcarpal, elbow, and small joints of the hand (PIP, DIP, MP). We aim to ascertain whether the corticosteroid and lidocaine injectate together is as effective as corticosteroid in the treatment of these tenosynovitides. For all these pathologies corticosteroid with or without lidocaine is standard of care for orthopaedic hand and shoulder surgeons and the use of either treatment regimen is based on personal preference by the surgeon.

Objectives:

1. Determine differences in pain scores / likert scale at the time of injection and during follow up in the corticosteroid plus lidocaine group as compared to the corticosteroid alone group.

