2. Determine differences in range of motion of the affected joint in the corticosteroid plus lidocaine group as compared to the corticosteroid alone group.
3. Determine differences in patient-reported outcome scores (VAS-pain, qDASH, PRWE, ASES, SF12, EQOL) in the corticosteroid plus lidocaine group as compared to the corticosteroid alone group.
4. Report patient characteristics associated with efficacy of addition of lidocaine to corticosteroid injectate for pain and ROM resolution (type of injury, affected joint, age, BMI, comorbidities, etc.).

Hypotheses:

Hypothesis⁰: Corticosteroid injectate alone will result in statistically significant reduced pain scores as compared to corticosteroid with lidocaine for the treatment of tenosynovitis.

Hypothesis¹: Lidocaine plus corticosteroid injectate will result in equivalent requirements for repeat injection or conversion to surgery as compared with corticosteroid injectate alone for the treatment of tenosynovitis.

Hypothesis²: Lidocaine plus corticosteroid injectate will result in equivalent patient reported outcomes scores as compared to corticosteroid alone for the treatment of tenosynovitis.

Hypothesis³: Lidocaine plus corticosteroid injectate will result in equivocal patient-reported outcome scores, ROM, and pain reduction as compared to corticosteroid alone for the treatment of tenosynovitis.

Study Design

This will be a randomized control trial of a group of patients with upper extremity tenosynovitides treated with either lidocaine plus corticosteroid or corticosteroid injection alone by upper extremity fellowship trained surgeons at Emory University. Patients will be randomly assigned to one of two groups at the time of treatment: 1. Lidocaine Plus Corticosteroid and 2. Corticosteroid Alone. A random allocation sequence, concealed in consecutively numbered, opaque, sealed envelopes, determining active treatment or placebo, will be computer generated. Written-informed consent will be obtained from patients prior to injection.

Patients in the Corticosteroid group will be treated with a 40 mg/mL injection of corticosteroid following sterile preparation. The volume of injectate differs for each tenosynovitis being treated. For example, trigger finger patients in the corticosteroid alone group will receive a 1mL of injectate total (consisting of 1 mL of 40mg/mL triamcinolone).

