As stated above, the first line treatment for trigger finger is corticosteroid injection with lidocaine, although there are a significant proportion of hand surgeons who inject corticosteroid alone. As no study has evaluated the efficacy of lidocaine mixed with the injectate versus corticosteroid alone, our study does not constitute deviation from current status quo of best medical practice for the treatment of trigger finger. **Both treatment options are considered standard of care and it is solely based on physician preference for which regimen is chosen as an injectate.** Patients will be notified of any potential risks with signed written consent as they would before any standard corticosteroid injection for the treatment of trigger finger. They will also be asked to sign an additional consent form agreeing to participate in our study outlining the nature of the study and the fact that no deviation from current best medical practice will occur throughout the course of the study.

Benefits to future subjects or science

By identifying whether or not lidocaine combined with corticosteroid injectate leads to improved patient outcomes as compared with corticosteroid injection alone, we will be able to educate physicians and patients on best medical practice for treatment of trigger finger. Additionally, as lidocaine has been reported to cause significant burning during injection, if there is no additional benefit to addition of lidocaine to corticosteroid injection, we will be able to spare future patients the discomfort of combining the injectate with lidocaine.

Data safety and monitoring plan:

Patients will be followed up closely in clinic at 2 weeks and 6 weeks post-injection to ensure patients did not experience side effects from the injection and to assess for efficacy of the injection. A low dose of corticosteroid and lidocaine is being utilized and we do not anticipate adverse effects.

Patients will have the ability to remove themselves from this study either completely or partially, and these options will be elucidated on the written consent form.

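### The hypotheses disagree on which arm must be shown not worse, and the one in the Precis cannot support leaving lidocaine out

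*Combined protocol and SAP*

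**What the plan says.** The aim is worded in several ways, all in the combined protocol and SAP:

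- **Precis/Abstract.** The arms are a "control group (corticosteroid injection alone) or the treatment group (lidocaine plus corticosteroid injection"). The hypothesis is "We hypothesize that those who receive lidocaine plus corticosteroid injection will be non-inferior in regards to pain", and likewise for range of motion, failure leading to surgery and patient-reported scores.
- **Lay Summary.** The direction is reversed: "Our study aims to determine if corticosteroid injection alone is as effective as corticosteroid combined with lidocaine".
- **Background and Significance.** The trigger finger text asks whether adding lidocaine improves outcomes, which is a superiority question. The later text on other conditions asks "whether the corticosteroid and lidocaine injectate together is as effective as corticosteroid in the treatment of these tenosynovitides", which is the Precis direction.
- **Hypotheses.** Hypothesis 0 reads "Corticosteroid injectate alone will result in statistically significant reduced pain scores as compared to corticosteroid with lidocaine". Hypotheses 1 and 2 claim equivalence for repeat injection or surgery and for patient-reported scores. Hypothesis 3 calls patient-reported scores, range of motion and pain reduction equivocal, which I read as no difference.
- **Benefits to future subjects or science.** After a sentence that leaves open whether lidocaine helps, it says "if there is no additional benefit to addition of lidocaine to corticosteroid injection, we will be able to spare future patients the discomfort".

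The Statistical Analysis section plans two-tailed difference tests at P < .05 and 95% confidence intervals. Its sample size of 63 is for detecting a 1-point difference in VAS-pain at the time of injection. No margin and no non-inferiority or equivalence test is given.

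**The concern.** Non-inferiority is a one-sided claim. If the combination is shown not worse than steroid alone, the only thing ruled out is that lidocaine does harm. The claim holds when lidocaine does nothing and also when it helps a great deal. To say that lidocaine can be left out, one must show that steroid alone is not worse than the combination. That is the Lay Summary's question, not the Precis's.

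Two readings of the results could then mislead. A met Precis hypothesis, or a non-significant two-sided test, could be taken as showing no additional benefit, and neither shows it. On pain, with Hypothesis 0 read as a prediction and no time points given, a result in any direction fits some stated hypothesis: steroid alone better fits Hypothesis 0, no difference fits Hypothesis 3, and lidocaine better fits the Precis.

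**Working it through.** **Inputs.** From Statistical Analysis: difference 1 VAS point, SD 2, n = 63, alpha 0.05 two-sided. Assumed, because not stated: 63 is per arm, allocation is 1:1, power is 80%, and margins are 0.5, 1.0 and 1.5 points tested at one-sided 2.5%. The SD is for pain at the time of injection; the documents give none for follow-up outcomes.

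**The plan's own figure.** n per arm = 2 × (1.96 + 0.842)² × 2² / 1² = 62.8, so 63. This reproduces the plan's number as a two-sided superiority size, not a non-inferiority size.

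**The two directions.** SE = 2 × √(2/63) = 0.356. Let b be the true VAS reduction due to lidocaine and m the margin.

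- P(combination shown not worse) = Φ((m + b)/SE − 1.96)
- P(steroid alone shown not worse) = Φ((m − b)/SE − 1.96)

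| Margin m | Benefit b | Combination not worse | Steroid alone not worse |
|---|---|---|---|
| 0.5 | 1 | 98.8% | 0.04% |
| 1.0 | 1 | 99.99% | 2.5% |
| 1.5 | 1 | over 99.99% | 28.9% |
| 0.5 | 0 | 28.9% | 28.9% |
| 1.0 | 0 | 80.1% | 80.1% |
| 1.5 | 0 | 98.8% | 98.8% |

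With a real benefit the two claims separate sharply. At a 1.5-point margin a 1-point benefit lies inside the margin, so the 28.9% there is not an error rate. When the arms are equal the two directions have the same probability, so reversing the direction costs no power in that case.

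**What a non-significant test shows.** At 63 per arm the 95% interval has half-width 1.96 × 0.356 = 0.70. An observed lidocaine advantage just under 0.70 is not significant, yet its interval runs up to about 1.40, beyond the 1 point the trial is sized to detect. For a true benefit of 0.5 (assumed), power is Φ(0.5/0.356 − 1.96) = 28.9%, so the test misses it about 71% of the time.

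**Pooled analysis.** With 1000 patients, 500 per arm and the same SD, SE = 2 × √(2/500) = 0.126. At a 0.5-point margin and equal arms, power is Φ(0.5/0.126 − 1.96) = about 97.7%. The difficulty with small margins therefore falls on the single-diagnosis subgroups.

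**The case against.** The strongest reply is that the Precis direction never reaches the analysis. The Objectives speak of determining differences, the tests are two-tailed, and the sample size is for detecting a difference. With a true 1-point benefit at 63 per arm, the planned comparison would find it with about 80% power. This stands. A reader might infer from the table that the trial as planned would overlook a lidocaine benefit. The documents do not support that, because the table describes a test that the plan does not run, with a margin that I assumed.

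A reader might also infer that dropping lidocaine is the planned conclusion. It is not. The benefits section is conditional, its preceding sentence is open in both directions, and a clear lidocaine benefit would make the condition fail. What remains is that the plan has no rule for deciding when the condition is met.

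The equivalence in Hypotheses 1 and 2 includes steroid alone being not worse, so part of the needed direction is already present. That also stands, but no equivalence test is planned, and the wording conflicts with the one-sided Precis claim for patient-reported scores.

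Finally, Hypothesis 0 carries a superscript zero and may be meant as a null hypothesis. Its mention of statistical significance makes that awkward, but the text does not settle it. The conflict with Hypothesis 3 is one of wording and may not be one of intent.

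**Conclusion.** The concern holds in a limited form and should be fixed. The protocol does not settle what is to be shown. Neither its Precis hypothesis nor a non-significant difference test can support the conditional statement about omitting lidocaine. The fault is in the hypothesis and the inference, not in the ability of the planned tests to reveal a difference.

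The logical point needs no figures. The 99.99% against 2.5% only illustrates it, under a 1-point margin, SD 2, 63 per arm and a 1-point benefit. It uses injection-time variability and does not measure what would happen for the follow-up outcomes.

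**What to change.** Reconcile the Lay Summary, Precis, Background, Hypotheses and benefits sections:

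1. For the follow-up outcomes, state the hypothesis as *corticosteroid alone is non-inferior to corticosteroid plus lidocaine*. Keeping the two-sided equivalence of Hypotheses 1 and 2 is a sound alternative, since it includes that direction.
2. Prespecify and justify a margin for each outcome the claim covers.
3. Add a rule: the conclusion that lidocaine adds no benefit is allowed only if the planned 95% confidence interval for the difference between arms excludes a disadvantage of steroid alone as large as the margin. A non-significant P value is not enough.
4. Tie Hypothesis 0 to VAS-pain at the time of injection, say whether it is a prediction or a null hypothesis, and limit the pain part of Hypothesis 3 to follow-up.

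The change adds no visits or data, but it is more than wording because margins must be chosen. With a small margin the single-diagnosis subgroups may be inconclusive. At an assumed 0.5 point, SD 2 and 63 per arm, power with equal arms is about 29%, and 80% power would need 252 per arm. State that limit in the plan rather than enrolling more patients to meet it.

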- Between the ages of 18 years and 95 years.

- For trigger finger: patients with a diagnosis of stenosing tenosynovitis based on a history of triggering and the presence of tenderness over the A1 pulley upon clinical examination. All patients, based on the Quinnell grading of trigger finger see in the figure below, will be included.

Grade	Clinical findings (during flexion and extension)
0	Normal movement
I	Uneven movement
II	Actively correctable
III	Passively correctable
IV	Fixed deformity

Exclusion Criteria:

- Patients who are minors, vulnerable subjects, or who are not willing to consent to participate in the study.
- Allergies to glucocorticoids, current daily use of glucocorticoids or strong opioids (morphine, fentanyl, hydromorphone, ketobemidone, methadone, nicomorphine, oxycodone, and meperidine), severe diabetic neuropathy of the hand influencing pain perception, rheumatoid arthritis, and neurological or psychiatric diseases, potentially influencing pain perception.
- Subjects who, in the opinion of the investigator, may be non-compliant with study schedules or procedures.

Statistical Analysis:

Data will be stored on an excel spreadsheet. We will collect the name, medical record number, age at time of surgery, ethnicity, gender, BMI, presence of diabetes, Quinnell grading of trigger finger, smoking status, pre-injection VAS-pain, post-injection VAS-pain, 10 point likert scale, complications, and need for repeat injection or surgical release. It is possible that other variables may be added depending on analysis. Each variable will be used as a nominal variable when possible (e.g. smoking status) or a continuous variable if needed (e.g. VAS-pain, patient related outcome scores). For some statistical calculations we may break up the continuous variables in to ranges (e.g. Ages 15-20, 25-30). We will perform statistical analysis using unpaired, 2-tailed Student t test to compare means for normally distributed data, Kruskal-Wallis test to compare medians of non-normally distributed data, and chi-square test to compare proportions. Statistical significance will be interpreted as $P < .05$. Confidence intervals will be calculated with a confidence level of 95%.

Specifically, the 2 groups will be compared using the Mann-Whitney U test to analyze the difference between the post-injection VAS scores. The Wilcoxon sign-rank test will be used to test the difference between the treatment and control group for pain and patient related outcomes.

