The minimally clinically important difference (MCID) varies for each outcome measure. Therefore, for the purposes of a power analysis, we will use the VAS-pain at the time of injection as the primary outcome. A similar study was published in 2017 from Earp *et al.* comparing needle-free jet lidocaine for pre-corticosteroid injection anesthesia with simultaneous lidocaine and corticosteroid injection. Using the results of this study as a metric, for the purposes of our study, to determine a 1-point change in VAS (4.5 to 3.5) with the reported standard deviation of 2 (SEM

was 0.4, with 30 subjects in each group) in the Earp *et al.* study, the number needed to treat to detect a difference between the treatment and placebo group would be 63 [32]. Therefore, we aim for a sample size of 63 patients for each possible tenosynovitis described in the inclusion criteria.

In total, **we plan to enroll 1000 patients total into this study** when combining all possible tenosynovitides encountered at Emory. These outcomes will be feasible to obtain in a reasonable time frame given the high volume of patients treated for tenosynovitis of all types at Emory. Patients will be grouped together for analysis and also broken into subgroups for sub-analysis based on primary diagnosis for injection.

JMP Pro Software or SPSS will be used to analyze the data and perform the statistics.

Risks to participation

Risks to participation include breach of confidentiality from PHI used to conduct the study. Every effort will be used to scrub data when possible and to use subject numbers/unique identifiers when possible.

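### Objective 4 asks whether the lidocaine effect varies by patient characteristic, but no planned method tests or estimates that variation

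*Combined protocol and SAP*

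**What the plan says.** Item 4 under Objectives is to "Report patient characteristics associated with efficacy of addition of lidocaine to corticosteroid injectate for pain and ROM resolution". It gives injury type, affected joint, age, BMI and comorbidities as examples and leaves the list open.

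Statistical Analysis names five tests:

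- where data are normal, a two-sided unpaired t test;
- where they are not, and for categorical outcomes: "Kruskal-Wallis test to compare medians of non-normally distributed data, and chi-square test to compare proportions";
- for VAS-pain after injection, a Mann-Whitney comparison of the two arms;
- for pain and the patient-reported scores: "The Wilcoxon sign-rank test will be used to test the difference between the treatment and control group for pain and patient related outcomes".

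Continuous variables may be cut into ranges, and further variables may be added. On subgroups, the same section says: "Patients will be grouped together for analysis and also broken into subgroups for sub-analysis based on primary diagnosis for injection".

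The document gives no regression model, interaction term, test of heterogeneity between subgroups, or rule for calling a characteristic a modifier. No analysis is tied to Objective 4 by name.

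**The concern.** In this trial the efficacy of adding lidocaine is the difference between the two arms. A characteristic is associated with that efficacy only if the difference changes across its levels, which is an arm-by-characteristic interaction. The named tests leave an analyst two obvious ways to attempt this, and neither addresses the question:

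- **Route A: compare outcomes by characteristic within the lidocaine arm.** The null is that the characteristic is unrelated to pain. A factor that raises pain equally in both arms will be flagged, although it says nothing about lidocaine.
- **Route B: compare the arms within each level and contrast the P values.** Each null is that lidocaine has no effect in that level. Whether one level is significant and the other is not depends heavily on how many patients each contains.

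This is not a multiplicity problem. It applies to one characteristic tested once. At stake is advice on which patients benefit from lidocaine: the section on benefits to future subjects says the results will be used to educate physicians and patients.

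**Working it through.** **Inputs from Statistical Analysis:** SD 2; design difference 1 VAS point (4.5 to 3.5); significance level 0.05; 63 as the required number; 1000 patients in total. **Assumptions, because the document is silent:** 1:1 allocation; 80% power behind the 63; SD 2 at every level; no dropout; a binary characteristic with 20% or 50% prevalence; prognostic shifts of 0.5 or 1 point.

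**1. The plan's own figure.** n per arm = 2 × (1.960 + 0.842)² × 2² / 1² = 62.8, so 63. The 63 is reproduced as a per-arm number for the main effect. The text can also be read as 63 patients per diagnosis; one diagnosis is taken below as 63 per arm, 126 in all. No figure is given for Objective 4.

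Power throughout is Φ(δ/SE − 1.96) + Φ(−δ/SE − 1.96).

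**2. Route A, no true modification, 1000 patients (500 in the lidocaine arm).**
- 20% prevalence, 100 v 400: SE = 2 × √(1/100 + 1/400) = 0.224. A 0.5-point prognostic shift gives 0.5/0.224 = 2.24, flagged in 61% of trials. A 1-point shift gives 4.47, flagged in 99%.
- 50% prevalence, 250 v 250: SE = 0.179. A 0.5-point shift is flagged in 80%.

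**3. Route B, no true modification.** With p1 and p2 the power in each level, the chance that exactly one is significant is p1(1 − p2) + p2(1 − p1). The SE in a level with n per arm is 2 × √(2/n).

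| Setting | Prevalence | p1, p2 | Discordant |
|---|---|---|---|
| 126 patients, uniform 1 point | 20% | 0.241, 0.709 | 61% |
| 126 patients, uniform 1 point | 50% | 0.510, 0.510 | 50% |
| 1000 patients, uniform 0.5 point | 20% | 0.424, 0.942 | 57% |
| 1000 patients, uniform 0.5 point | 50% | 0.798, 0.798 | 32% |
| 1000 patients, uniform 1 point | 20% | 0.942, 1.000 | 6% |
| 1000 patients, uniform 1 point | 50% | 1.000, 1.000 | 0% |

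**4. Interaction test, no true modification.** By construction it rejects in 5% of trials. In simulations of 4000 trials per setting, with a 1-point prognostic factor and a uniform 1-point lidocaine effect, it rejected in 4.7-5.6%.

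**5. Power of the interaction test.** SE = 2 × √(2/n1 + 2/n2), with n1 and n2 the patients per arm in each level. For 1000 patients at 20% prevalence: 2 × √(2/100 + 2/400) = 0.316, and 1/0.316 = 3.16 gives 89%.

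| Patients | True difference in effect | Power, 20% prevalence | Power, 50% prevalence |
|---|---|---|---|
| 1000 | 1 point | 89% | 98% |
| 1000 | 0.5 point | 35% | 51% |
| 126 | 1 point | 20% | 29% |

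**The case against.** The strongest reply is that the plan does not specify a wrong analysis. It specifies none for Objective 4. The document describes neither testing by characteristic within one arm nor contrasting P values between strata. The verb in Objective 4 is to report, where Objectives 1 to 3 say determine, and none of the four hypotheses concerns characteristics, so an exploratory reading is plausible. This stands: misattribution is a risk, not a certainty, and an exploratory label is right. It does not remove the gap. A descriptive report of lidocaine efficacy by characteristic still has to describe the between-arm difference by characteristic.

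A reader might infer more than the document supports:

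- *That every named test compares just two groups.* Kruskal-Wallis and chi-square can take more, and the signed-rank test is a paired test. The accurate statement is that none tests whether the arm difference varies.
- *That the two routes cannot find true modifiers.* Take 1000 patients at 20% prevalence. Where lidocaine has no effect in one level and a 1-point effect in the other, Route B detects this about as often as the interaction test (89% v 88% in simulation). It fails, at about 0% v 88%, when the effects are 1 and 2 points. Route A falls to 5% only when a prognostic shift exactly cancels the modification. With a 1-point modification and no shift its power is 99%, and 61% with a 0.5-point shift. The fault is that these routes do not isolate modification, not that they never respond to it.
- *That diabetes would be mislabelled.* The Background links diabetes to how often trigger finger occurs, not to pain after injection.

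**Conclusion.** The point holds as an omission that carries a risk. Objective 4 is an interaction question, and no planned method tests or estimates an interaction. The size of the risk depends on how the named tests are used. It is large for within-arm comparisons (61% at a 0.5-point shift, 20% prevalence, 1000 patients) and for P-value contrasts within one diagnosis (50-61%) or in the pooled sample with a half-point effect (32-57%). It is small (0-6%) for P-value contrasts in the pooled 1000 if lidocaine has a uniform effect of the full design size. These figures rest on the assumed prevalences, shifts and 1:1 allocation, and on the plan's SD of 2 applying in every subgroup. The primary comparison of VAS-pain at injection is not affected. The change is worth making because a stated objective otherwise has no analysis that answers it.

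**What to change.** Add to Statistical Analysis:

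- Objective 4 is addressed, for each characteristic it lists (injury type, affected joint, age, BMI, comorbidities), by a linear regression of VAS-pain and of ROM on arm, the characteristic and arm × characteristic, in all randomised patients. There is one model per characteristic and outcome. Characteristics stay continuous where possible.
- The interaction estimate is reported with its 95% CI and labelled exploratory.
- Within-arm associations and contrasts of within-subgroup P values are not used to claim that a characteristic modifies the lidocaine effect.
- A null interaction is not read as absence of modification.

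The list of comorbidities and the VAS and ROM time points should be fixed in the same text.

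The cost is a few sentences and simple regressions in JMP or SPSS, which are already planned. No patients or visits are added. Age, BMI, diabetes and smoking are already on the data list. ROM is promised at 6 weeks in the abstract but is not on that list, nor is affected joint, so both should be added, and ROM needs a definition that is comparable across joints before it is pooled. The real downside is precision: intervals will be wide within a single diagnosis and for half-point differences even in the full sample, so few modifiers are likely to be established.
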